3.2.1 Hematologic exceptions

- Grade 3 or 4 lymphocytopenia without clinical signs of infection grade 2 or above.
 - Lenalidomide, romidepsin and CC-486 (5-azacitidine) will be continued in the event of asymptomatic grade 3 or 4 lymphocytopenia, unless there are clinical signs of significant infection (persistent fevers, labile blood pressure, localized complaints or findings on physical examination, hypoxia or organ dysfunction).
- Grade 3 neutropenia without clinical signs of infection grade 2 or above.
 - Lenalidomide, romidepsin and CC-486 (5-azacitidine) will be continued in the event of grade 3 neutropenia unless there are clinical signs of significant infection, as listed above.
- Grade 3 thrombocytopenia without signs of bleeding that resolved within 7 days of holding the study drug(s) (See Section 3.5.1 for study drug holding parameters).
- Grade 3 anemia that improves to Grade ≤ 2 after transfusion of up to two units of pRBCs and does not recur within 7 days.
- Grade 3 febrile neutropenia (grade 3 febrile neutropenia at any time during therapy will be considered an SAE but not DLT)

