3.2 DOSE LIMITING TOXICITY

A dose-limiting toxicity (DLT) is defined as: any treatment-emergent and related severe (grade \geq 3) toxicity, i.e., toxicity deemed related to lenalidomide, romidepsin and/or CC-486 (5-azacitidine) by the PI or designee and occurring during the MTD observation time, defined as day -7 until end of cycle 1 (normally day 22). Each patient must receive all doses of the investigational medications during cycle 1 to be considered as successfully completing the DLT evaluation period.

The following toxicities and conditions will be recorded, however they will not be considered to be DLTs:

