3.2.2 Non-Hematologic exceptions

- Transient (< 72 hours) grade 3 hypoalbuminemia, hypokalemia, hypomagnesemia, hyponatremia or hypophosphatemia which responds to medical intervention. Lenalidomide, romidepsin and CC-486 (5-azacitidine) will be continued while the metabolic abnormalities are corrected by intravenous or oral supplementation
- Patients who require short term hospitalization (3 days or less) only for fluid and electrolyte disturbances secondary to anorexia, nausea/vomiting/diarrhea which are common AEs for 5-azacitidine, lenalidomide and romidepsin individually and more so for the combination. This exception does not apply to secondary organ dysfunction resulting from this biochemical derangements or patients that require vasopressor BP support.

- Grade 3 rash that resolves to grade ≤ 2 within 7 days of holding the study drug(s) (See Section 3.5.1 for study drug holding parameters).

Management and dose modifications associated with the above adverse events are outlined in Section 3.5. Occurrence of any DLT-defining toxicity after the first 28 days of treatment will lead to dose modification as specified below; however, it will not be deemed a DLT for purposes of dose escalation.

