3.5.1 Treatment modifications for adverse reactions

All treatment modifications should be discussed with the senior clinical investigators on the study. Treatment modifications will follow the guidelines outlined in [Table 6](#). Any given dose modification after Cycle 1 can be repeated twice in a patient as long as the patient is benefiting from therapy and does not meet off-treatment criteria.

If a toxicity which requires modification of therapy per [Table 6](#) occurs during the window period (day -7 to day -1) and does not meet the definition of a DLT, cycle 1 day 1 may start after resolution to grade ≤ 1 (grade ≤ 2 for anemia).

All grading scales in the following tables are according to the revised NCI Common Terminology Criteria for Adverse Events (CTCAE) version 5.0.

Table 6: Dose Modification of Lenalidomide, romidepsin and CC-486 (5-azacitidine) for treatment related AEs

Event	Initial management	Follow-up Management
Cycle 1 DLT Evaluation Period		
Grade 1 AEs		
Any AE	Continue treatment	Continue monitoring and laboratories at least once weekly
Grade 2 AEs		
ANC: $<1.5 - 1.0 \times 10^9/L$	Continue treatment	Monitor cell counts at least twice weekly Pegfilgrastim*

Event	Initial management	Follow-up Management
Platelet: < 75,000 - 50,000/mcL	Consider holding treatment for up to 7 days	Monitor cell counts at least twice weekly Restart treatment when platelet count >75,000/mcL
Hgb: < 10.0 - 8.0g/dL	Continue treatment	Monitor cell counts at least twice weekly Consider transfusion before cycle 2
Any other AE	Continue treatment	Continue monitoring and laboratories once weekly
Grade 3 AEs		
ANC: <1.0 -0.5 x 10⁹/L	Hold treatment for up to 7 days Restart treatment at full doses	Monitor cell counts at least twice weekly G-CSF# and Pegfilgrastim*;
Platelet: <50,000 - 25,000/mcL	Hold treatment for up to 7 days Restart treatment at when platelets > 75,000/mcL	Monitor cell counts at least twice weekly If platelets are not > 75,000/mcL the patient is off treatment DLT
Hgb < 8.0g/dL	Hold treatment for up to 7 days Restart treatment after transfusion	Monitor cell counts at least twice weekly Transfusion until Hgb > 9 g/L
Any other AE	Hold treatment for up to 7 days Restart treatment when AE has resolved to ≤ grade 1	Continue monitoring and laboratories at least twice weekly If the AE has not improved to ≤ grade 1, the patient is off treatment DLT
Grade 4 AEs at any time during cycle 1		
Any AE	Discontinue treatment	Off treatment DLT
Cycles 2 through 6		

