6.1.2 Data Collection/Recording Exceptions

6.1.2.1 Abnormal Laboratory Values

An abnormal laboratory value will be recorded as an AE **only** if the laboratory abnormality is characterized by any of the following:

- Results in discontinuation from the study
- Is associated with clinical signs or symptoms
- Requires treatment or any other therapeutic intervention
- Is associated with death or another serious adverse event, including hospitalization
- Is judged by the Investigator to be of significant clinical impact
- If any abnormal laboratory result is considered clinically significant, the investigator will provide details about the action taken with respect to the test drug and about the patient's outcome.

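### Cycle-1 grade 3 neutropenia without infection: Section 3.2.1 continues all three drugs, Table 6 holds them for up to 7 days

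*Combined protocol and SAP*

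**What the plan says.** Section 3.2 lists events that are exempt from being DLTs, introduced by "The following toxicities and conditions will be recorded, however they will not be considered to be DLTs". Three of these exceptions also carry a dosing order of their own:

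- Grade 3 neutropenia (3.2.1): "Lenalidomide, romidepsin and CC-486 (5-azacitidine) will be continued in the event of grade 3 neutropenia unless there are clinical signs of significant infection".
- Lymphocytopenia (3.2.1): the three drugs "will be continued in the event of asymptomatic grade 3 or 4 lymphocytopenia", again unless there are signs of significant infection.
- Transient (under 72 hours) grade 3 electrolyte or albumin abnormalities (3.2.2): the drugs "will be continued while the metabolic abnormalities are corrected by intravenous or oral supplementation".

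Table 6 in Section 3.5.1 covers the same three drugs for treatment-related events and has a separate cycle-1 block:

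- Grade 3 ANC: "Hold treatment for up to 7 days Restart treatment at full doses".
- Grade 3, any other AE: "Hold treatment for up to 7 days Restart treatment when AE has resolved to ≤ grade 1". Failure to reach grade 1 means off treatment and a DLT.
- "Grade 4 AEs at any time during cycle 1": any AE means discontinuation and a DLT.

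Section 3.2.2 closes by referring management of the listed events to Section 3.5. Section 3.4.2 also points to 3.5 for dose modifications, and 3.5.1 says that modifications follow Table 6. None of these sentences says which text prevails if they differ.

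**The concern.** A grade 3 neutrophil count in cycle 1, without infection and related to treatment, is named specifically in both places and receives opposite orders. The investigator has to decide whether to give the remaining cycle-1 drugs on time or to stop them for up to a week, and the protocol supports either action. At stake are consistent safety management and consistent cycle-1 exposure within a small expansion cohort (up to 6 additional evaluable patients, Section 2.5.1). Section 2.5.2 does not mark Arm 3 as closed, so the instruction may still be needed.

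**Working it through.** The plan gives no figure on this point, so the check is a comparison of the texts followed by simple day-counting for one patient.

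**Comparison**

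| Event in cycle 1 | Section 3.2 | Table 6, cycle 1 | How firm |
|---|---|---|---|
| Grade 3 neutropenia, no significant infection | Continue | Hold up to 7 days (specific ANC row) | Direct conflict |
| Transient grade 3 electrolyte or albumin change | Continue during supplementation | Hold until grade 1 or lower (catch-all row) | Secondary |
| Asymptomatic grade 3 lymphocytopenia | Continue | Hold (catch-all row) | Less certain |
| Asymptomatic grade 4 lymphocytopenia | Continue; not a DLT | Discontinue; DLT (catch-all row) | Less certain |

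**Is the neutropenia conflict an artefact of later cycles?** No. Table 6 has its own block for cycles 2 to 6, where a first grade 3 ANC event means continuing treatment with G-CSF support. The table therefore separates cycle 1 (hold) from later cycles (continue). Nor is the cycle-1 hold worded as optional: the grade 2 platelet row only asks staff to consider holding, while the grade 3 ANC row orders it.

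**Why lymphocytopenia is less certain.** Section 6.1.2.1 says "An abnormal laboratory value will be recorded as an AE" only under listed conditions, such as symptoms or a need for treatment. An untreated, asymptomatic lymphocyte count may meet none of them, and then the catch-all rows are not triggered. Section 3.2 does say that its exceptions are recorded, which leaves the matter open. Electrolyte changes that are supplemented do meet the treatment condition, so 6.1.2.1 does not remove that mismatch.

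**DLT status.** For uninfected grade 3 neutropenia the two texts agree: 3.2.1 exempts it, and the ANC row does not call it a DLT. The label differs only for grade 4 lymphocytopenia.

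**Dosing in one affected patient.** Inputs: oral drugs on days 1 to 10 and romidepsin 12 mg/m² on days 1 and 10 (Table 4); CBC and chemistry on days 1 and 10 of cycle 1 (Section 3.9); pre-dose check up to 3 days before romidepsin (Section 3.7); 28-day cycle. Assume that romidepsin is planned for day 10, that the event is found on day d before that day's oral dose, and that held doses resume after the hold.

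- Check day: d = 7, 8, 9 or 10.
- Oral days still to come: 11 − d = 4, 3, 2, 1 of 10 (40%, 30%, 20%, 10%).
- Romidepsin still to come: 12 of 24 mg/m² = 50%.
- Restart after a full 7-day hold: d + 7 = day 14, 15, 16, 17.
- Last oral dose after such a hold: (d + 7) + (11 − d) − 1 = day 17 for every d, instead of day 10.
- Days left in the cycle after that: 28 − 17 = 11.

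The 40% to 10% range is not a bound. Table 6 asks for laboratory tests at least weekly for grade 1 events and counts at least twice weekly for grade 2 ANC, so detection can be earlier. On day 4, for example, 11 − 4 = 7 of 10 oral days would remain. An event first found after the last cycle-1 dose changes no dosing.

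**Background frequency.** Table 5.1 reports grade 3 neutropenia in 15 patients on romidepsin plus lenalidomide: 15/49 = 31%, with the denominator inferred from the printed percentages. That is another regimen and schedule, and infected and uninfected cases are not separated. It shows that the event occurs and is not a cycle-1 rate for Arm 3.

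**The case against.** The strongest reply is that Section 3.2 only defines DLTs and that the protocol assigns dosing to Section 3.5. Three pointers run to 3.5 and none runs back, and the one closing 3.2.2 refers to these very exceptions. Modifications are also to be discussed with senior investigators (3.5.1), and the team meets weekly (7.4.1). Most of this stands: Table 6 is the likelier intention, and the oversight limits harm. It does not remove the conflict. The thrombocytopenia and rash bullets send the reader to 3.5.1 for holding, whereas the neutropenia bullet carries its own contrary order. If Table 6 governs, that sentence is wrong.

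For the catch-all rows, a reader could let the specific text in 3.2 override the generic row. That is reasonable, and it is why those mismatches are secondary.

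Three stronger readings are tempting but not supported:

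- *Held patients become unevaluable.* Section 3.2 requires all cycle-1 doses, and 10.3.4 replaces a patient without DLT who did not finish cycle 1. But the ANC row restarts at full doses, and the remaining doses fit within 28 days. Late completion is still completion. Evaluability would be lost only if held doses were never given, which the documents do not say.
- *A full hold breaches the romidepsin window.* Restart on days 14 to 17 falls after day 12 (day 10 + 2), but nothing shows that this scheduling window caps a hold for toxicity. The original design allowed a 7-day delay in completing cycle 1 (3.4.1).
- *The MTD is in doubt.* Escalation is complete, 20 mg is declared, and both texts give the neutropenia event the same DLT status. The differing label for grade 4 lymphocytopenia feeds no dose-decision rule stated for Arm 3.

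**Conclusion.** The neutropenia conflict is real and rests on the text alone: same event, grade, cycle and drugs, with opposite orders and no rule of precedence. The electrolyte/albumin and lymphocytopenia mismatches are secondary because they arise only through catch-all rows, and the lymphocytopenia rows may not be triggered at all.

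The effect is on cycle-1 dosing and safety management in Arm 3. Under the day-10 assumption, an affected patient found at the scheduled pre-dose check has half the cycle's romidepsin and 40% to 10% of the oral days either given on time or delayed by up to 7 days. How many patients would be affected cannot be stated, because neither the number still to start nor the cycle-1 event rate in this regimen is in the documents. This is an inconsistency of wording that should be corrected; no defect in the escalation design follows from it.

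**What to change.** Give one instruction for cycle-1 grade 3 ANC in both places. The clinical team chooses which:

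1. If Table 6 is intended, replace the continue sentence in the 3.2.1 neutropenia bullet with a reference to 3.5.1 for holding, as the thrombocytopenia bullet already has.
2. If continuing is intended, change the Table 6 cycle-1 grade 3 ANC row to: *Continue unless there are clinical signs of significant infection; then hold for up to 7 days.*

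Separately, keep the continue sentences for lymphocytopenia (3.2.1) and metabolic changes (3.2.2), and add matching exceptions to Table 6, cycle 1:

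- Grade 3 any-other-AE row and grade 4 any-AE row: *except asymptomatic lymphocytopenia without clinical signs of significant infection (continue; not a DLT if without clinical signs of infection grade 2 or above, per 3.2.1).*
- Grade 3 any-other-AE row: *except the metabolic abnormalities named in 3.2.2, for which treatment continues during supplementation; hold if not corrected within 72 hours.* The last clause is needed because whether an abnormality is transient is known only afterwards.

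The cost is a few lines in the next amendment, with no added patients, visits, tests or data.

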3.2.2 Non-Hematologic exceptions

- Transient (< 72 hours) grade 3 hypoalbuminemia, hypokalemia, hypomagnesemia, hyponatremia or hypophosphatemia which responds to medical intervention. Lenalidomide, romidepsin and CC-486 (5-azacitidine) will be continued while the metabolic abnormalities are corrected by intravenous or oral supplementation
- Patients who require short term hospitalization (3 days or less) only for fluid and electrolyte disturbances secondary to anorexia, nausea/vomiting/diarrhea which are common AEs for 5-azacitidine, lenalidomide and romidepsin individually and more so for the combination. This exception does not apply to secondary organ dysfunction resulting from this biochemical derangements or patients that require vasopressor BP support.

- Grade 3 rash that resolves to grade ≤ 2 within 7 days of holding the study drug(s) (See Section 3.5.1 for study drug holding parameters).

Management and dose modifications associated with the above adverse events are outlined in Section 3.5. Occurrence of any DLT-defining toxicity after the first 28 days of treatment will lead to dose modification as specified below; however, it will not be deemed a DLT for purposes of dose escalation.

3.3 DOSE ESCALATION

Dose escalation will proceed according to the following schedule (Table 2). Dose escalation will follow the following guidelines (Table 3). Each patient will continue treatment at the dose level they were enrolled – there will be no intra-patient dose escalation. In case of severe toxicity, the lenalidomide dose should be reduced by one dose level, dose adaption of the other drugs as per investigators discretion.

The MTD is the dose level at which no more than 1 of up to 6 patients experience DLT during the DLT evaluation window(s), or the dose below that at which at least 2 (of ≤ 6) patients have DLT. The protocol will be amended to note the MTD once determined.

NOTE: If enrollment to the current or next higher dose level cannot proceed because a patient at the current dose level is still within the DLT window, screened patients who are in need of urgent treatment may be enrolled at the next lower dose level as long as the ≤ 6 patient limit per dose level is maintained. In the event that these additionally enrolled patients experience DLT(s) after formal evaluation of dose level determinations has taken place, the Principal Investigator will review and assess if any changes to the ongoing protocol/dose escalation or safety parameters need to be considered.

NOTE: After the dose escalation portion was completed, the MTD of lenalidomide was determined to be 20mg.

Table 2: Lenalidomide Dose Escalation Schedule

Dose Level	Lenalidomide
Level -2	0 mg
Level -1	2.5 mg
Level 1	5mg – Starting dose
Level 2	10mg
Level 3	15mg
Level 4	20mg

Table 3: Dose Escalation Guidelines

Number of Patients with DLT at a Given Dose Level	Escalation Decision Rule
0 out of 3	Enter 3 patients at the next dose level.

Number of Patients with DLT at a Given Dose Level	Escalation Decision Rule
≥ 2	Dose escalation will be stopped. This dose level will be declared the maximally administered dose (highest dose administered). Three (3) additional patients will be entered at the next lowest dose level if only 3 patients were treated previously at that dose.
1 out of 3	Enter at least 3 more patients at this dose level. 
• If 0 of these 3 patients experience DLT, proceed to the next dose level.• If 1 or more of this group suffer DLT, then dose escalation is stopped, and this dose is declared the maximally administered dose. Three (3) additional patients will be entered at the next lowest dose level if only 3 patients were treated previously at that dose.
≤ 1 out of 6 at highest dose level below the maximally administered dose	This is generally the recommended phase 2 dose. At least 6 patients must be entered at the recommended phase 2 dose.

3.4 DRUG ADMINISTRATION

3.4.1 Summary of Original Study Design

Prior to approval of Amendment dated 12/07/2022, the original study design included a 7 day lead-in window of lenalidomide monotherapy to assess early clinical activity of this agent prior to combination therapy.

The standard treatment cycle was 21 days (3 weeks), except for the first cycle where we had 7 days lead in phase for lenalidomide (lead in was allowed to be shorter for patients requiring urgent treatment with the four-drug combination due to rapid disease progression, at PI discretion). The maximum allowable delay for completion of cycle 1 treatment was 1 week (7 days) in order to best assess the tolerability of this treatment. The maximum allowable delay for completion of treatment in all subsequent cycles was 3 weeks (21 days). The minimum window between initiation of new cycles was 19 days. For the dose escalation Cohort 1, treatment was administered on an inpatient basis during the first 2 days (after lead-in period) of the first cycle, and as outpatient during subsequent weeks and cycles unless decided otherwise by the principal investigator based on clinical judgment.

After 20 patients were enrolled and the dose escalation Cohort 1 Arm 1 was fully accrued, the study design was modified to remove the 7 day lenalidomide window (Amendment 12/07/2022).

3.4.2 Summary of Current Study Design (as of Amendment 12/07/2022)

For the Dose Expansion Cohort 2 Arm 3, treatment will be administered as outpatient for all cycles unless decided otherwise by the principal investigator based on clinical judgment. The standard treatment cycle will be 28 days (4 weeks). Reported adverse events and potential risks are described in Section 14. Appropriate dose modifications are described in Section 3.5. No investigational or commercial agents or therapies other than those described below may be administered during the study therapy period with the intent to treat the patient's malignancy. See **Table 4** below for description of drug regimen.

A cycle may be delayed for the following reasons:

- Scheduling or other administrative reasons (no more than 14 days)
- Administration of COVID-19 vaccination (if the delay would not result in more than 6 weeks treatment-free period)
- Toxicity/dose management as defined below

Table 4: Drug Regimen

Agent	Premedications; Precautions	Dose	Route	Schedule
Lenalidomide	Aspirin for thrombosis prophylaxis	As per dose level***	Oral	Days 1 to 10
Romidepsin	Premedicate with ondansetron or granisetron *	12mg/ m ² in 500 mL NS	IV over 4 hours	Days 1 and 10 (± 2 days)
CC-486 (5-azacitidine)	Premedicate with ondansetron or granisetron **	300mg	Oral	Days 1 to 10
Dexamethasone	No premedication	40mg	Oral	Days 1 and 10 (± 2 days)

* Mandatory for the first cycle; subsequently based on clinical judgement
** Not mandatory, administer based on clinical judgement
*** Doses as appropriate for assigned dose level

For a full detailed product description and administration guidelines, see Section 14. Infusions may be done peripherally or via central venous access device (if present; not required to be placed by the study).

NOTE: Cycles beyond Cycle 1 may not commence until the laboratory criteria in Section 2.1.1.8 are met and non-laboratory treatment-emergent AEs have resolved to grade ≤2 (grade ≤1 if at related to treatment).

3.4.3 Agent-specific Information and Instructions

3.4.3.1 Lenalidomide

Patients will receive lenalidomide for 10 days through Cycles 1-6 of treatment (see schema Section 3.1).

Lenalidomide is administered orally once daily and should be taken around the same time each day with at least 8 ounces of water. The capsules must be swallowed whole and may be taken with or without food.

3.4.3.2 Romidepsin

Romidepsin will be administered on day 1 and 10 of each cycle through a peripheral or central intravenous catheter over 4 hour period. If patients are also taking antiemetics to relieve the side effects associated with romidepsin these should be administered at least 60 minutes before the romidepsin. Patients concurrently receiving romidepsin and warfarin should have PT and INR

levels checked more frequently. The use of rifampin and CYP3A inducers should be avoided for the duration of the study (see Section [4](#) and [Appendix C](#)).

